13. APPENDICES

13.1. List of statistical tables, figures and listings

Study Number: LPH-2202

BASICC

File (BASICC)	Type	Number	Title	Mock
STUDY PATIENTS				
T_14_1_1_1_ds_enrl.rtf	Table	14.1.1.1	Patients' disposition – Enrolled patients	T1
F_14_1_1_1_ds_enrl.rtf	Figure	14.1.1.1	Patients' disposition – Enrolled patients	F1
T_14_1_1_2_1_dv_incl.rtf	Table	14.1.1.2.1	Summary of protocol deviations by category and type – Included patients	T2
L_14_1_1_2_1_dv_incl.rtf	Listing	14.1.1.2.1	Patients with at least one protocol deviation – Included patients	L1
T_14_1_1_2_2_disc_incl.rtf	Table	14.1.1.2.2	Premature withdrawal – Reason of withdrawal	Т3
L_14_1_1_2_2_disc_incl.rtf	Listing	14.1.1.2.2	Patients prematurely withdrawn – Included patients	L2
DEMOGRAPHIC AND OTHER	BASELIN	E CHARACTER	ISTICS, COMPLIANCE, STUDY DURATION	
T_14_1_2_1_1_dm_saf.rtf	Table	14.1.2.1.1	Demographic characteristics – Safety Set	T4
T_14_1_2_1_2_dm_fas.rtf	Table	14.1.2.1.2	Demographic characteristics – Full Analysis Set	T4
T_14_1_2_2_1_1_prevm_saf.rtf	Table	14.1.2.2.1.1	Summary of previous medications – Safety Set	T5
T_14_1_2_2_1_2_prevm_fas.rtf	Table	14.1.2.2.1.2	Summary of previous medications – Full Analysis Set	T5
T_14_1_2_2_1_forbidm_saf.rtf	Table	14.1.2.2.2.1	Past or concomitant forbidden medications at baseline – Safety Set	Т6
T_14_1_2_2_2_forbidm_fas.rtf	Table	14.1.2.2.2.2	Past or concomitant forbidden medications at baseline – Full Analysis Set	Т6
T_14_1_2_2_3_1_cmbl_saf.rtf	Table	14.1.2.2.3.1	Concomitant treatments for first symptoms of infectious rhinitis at baseline – Safety Set	Т7
T_14_1_2_2_3_2_cmbl_fas.rtf	Table	14.1.2.2.3.2	Concomitant treatments for first symptoms of infectious rhinitis at baseline – Full Analysis Set	Т7
T_14_1_2_3_1_mh_saf.rtf	Table	14.1.2.3.1	Medical and surgical past history – Safety Set	Т8

AXIODIS CRO 26/47

Study Number: LPH-2202

BASICC

Statistical Analysis Plan
Final version – August 09th, 2023

File (BASICC)	Туре	Number	Title	Mock
T 14 1 2 3 2 mh fas.rtf	Table	14.1.2.3.2	Medical and surgical past history – Full Analysis Set	Т8
T 14 1 2 4 1 arssqbl_saf.rtf	Table	14.1.2.4.1	Acute Rhinitis Symptoms Severity Questionnaire at baseline – Safety Set	Т9
T 14 1 2 4 2 arssqbl fas.rtf	Table	14.1.2.4.2	Acute Rhinitis Symptoms Severity Questionnaire at baseline – Full Analysis Set	Т9
T 14 1 2 5 1 fever saf.rtf	Table	14.1.2.5.1	Fever and body temperature at baseline – Safety Set	T10
T_14_1_2_5_2_fever_fas.rtf	Table	14.1.2.5.2	Fever and body temperature at baseline – Full Analysis Set	T10
T_14_1_3_compl_saf.rtf	Table	14.1.3	Summary of compliance per treatment group – Safety Set	T11
T_14_1_4_stdur_saf.rtf	Table	14.1.4	Treatment and study durations by patient – Safety Set	T12
EFFICACY		_		
T 14 2 1 1 aucarssq_fas.rtf	Table	14.2.1.1	AUC on global score of ARSSQ per treatment group – Full Analysis Set	T13
T_14_2_1_2_aucarssq_pp.rtf	Table	14.2.1.2	AUC on global score of ARSSQ per treatment group – Per Protocol Set	T13
F 14 2 1 1 aucarssq_fas.rtf	Figure	14.2.1.1	Boxplots of AUC on global score of ARSSQ by treatment group – Full Analysis Set	F2
F 14 2 1 2 aucarssq pp.rtf	Figure	14.2.1.2	Boxplots of AUC on global score of ARSSQ by treatment group – Per Protocol Set	F2
T_14_2_2_1_1_ancovarssq_fas.rtf	Table	14.2.2.1.1	Multivariate ANCOVA model for the AUC on global score of ARSSQ – Full Analysis Set	T14
T 14 2 2 1 2 ancovarssq pp.rtf	Table	14.2.2.1.2	Multivariate ANCOVA model for the AUC on global score of ARSSQ – Per Protocol Set	T14
T_14_2_2_1_coxcc_fas.rtf	Table	14.2.2.2.1	Cox survival regression model for the duration of common cold – Full Analysis Set	T15
F_14_2_2_2_1_1_hrcc_fas.rtf	Figure	14.2.2.2.1.1	Forest plot of Hazard Ratios from final multivariate Cox survival regression model for the duration of common cold – Full Analysis Set	F3
F_14_2_2_2_1_2_kmcc_fas.rtf	Figure	14.2.2.2.1.2	Kaplan-Meier graph for the duration of common cold by treatment group – Full Analysis Set	F4
T_14_2_2_2_coxcs_fas.rtf	Table	14.2.2.2.2	Cox survival regression model for the duration of cold symptoms – Full Analysis Set	T15

AXIODIS CRO 27/47

File (BASICC)	Type	Number	Title	Mock
F_14_2_2_2_1_hrcs_fas.rtf	Figure	14.2.2.2.1	Forest plot of Hazard Ratios from final multivariate Cox survival regression model for the duration of cold symptoms – Full Analysis Set	F3
F_14_2_2_2_2_kmcs_fas.rtf	Figure	14.2.2.2.2	Kaplan-Meier graph for the duration of cold symptoms by treatment group – Full Analysis Set	F4
T_14_2_2_3_coxqol_fas.rtf	Table	14.2.2.2.3	Cox survival regression model for the duration of impact on Quality-of-Life – Full Analysis Set	T15
F_14_2_2_2_3_1_hrqol_fas.rtf	Figure	14.2.2.2.3.1	Forest plot of Hazard Ratios from final multivariate Cox survival regression model for the duration of impact on Quality-of-Life – Full Analysis Set	F3
F_14_2_2_2_3_2_kmqol_fas.rtf	Figure	14.2.2.3.2	Kaplan-Meier graph for the duration of impact on Quality-of-Life by treatment group – Full Analysis Set	F4
T_14_2_2_3_1_cccmed_fas.rtf	Table	14.2.2.3.1	Impact of the treatment on the intake of conventional common cold medications – Full Analysis Set	T16
T 14 2 2 3 2 antibio fas.rtf	Table	14.2.2.3.2	Impact of the treatment on the intake of antibiotics – Full Analysis Set	T16
T_14_2_2_3_3_antipyr_fas.rtf	Table	14.2.2.3.3	Impact of the treatment on the intake of antipyretics – Full Analysis Set	T16
T_14_2_2_3_4_mucol_fas.rtf	Table	14.2.2.3.4	Impact of the treatment on the intake of mucolytics – Full Analysis Set	T16
T 14 2 2 3 5 decong fas.rtf	Table	14.2.2.3.5	Impact of the treatment on the intake of decongestants – Full Analysis Set	T16
T_14_2_2_3_6_antitus_fas.rtf	Table	14.2.2.3.6	Impact of the treatment on the intake of antitussives – Full Analysis Set	T16
T_14_2_2_3_7_cortico_fas.rtf	Table	14.2.2.3.7	Impact of the treatment on the intake of systemic and topical corticosteroids – Full Analysis Set	T16
T_14_2_3_cm_fas.rtf	Table	14.2.3	Concomitant treatments – Full Analysis Set	T5
T 14 2 4 1 1 1 ae saf.rtf	Table	14.2.4.1.1.1	Summary of non-related adverse events – Safety Set	T17
T 14 2 4 1 1 2 ae fas.rtf	Table	14.2.4.1.1.2	Summary of non-related adverse events – Full Analysis Set	T17

AXIODIS CRO 28/47

Final version – August 09th, 2023

File (BASICC)	Type	Number	Title	Mock
T_14_2_4_1_2_1_trtae_saf.rtf	Table	14.2.4.1.2.1	Non-related treatment-emergent adverse events by System Organ Class and Preferred Term – Safety Set	T18
T_14_2_4_1_2_2_trtae_fas.rtf	Table	14.2.4.1.2.2	Non-related treatment-emergent adverse events by System Organ Class and Preferred Term – Full Analysis Set	T18
L_14_2_4_2_1_1_sae_saf.rtf	Listing	14.2.4.2.1.1	Serious non-related adverse events – Safety Set	L3
L_14_2_4_2_1_2_sae_fas.rtf	Listing	14.2.4.2.1.2	Serious non-related adverse events – Full Analysis Set	L3
L_14_2_4_2_2_1_aedisct_saf.rtf	Listing	14.2.4.2.2.1	Non-related adverse events leading to definitive discontinuation of the trial device – Safety Set	L3
L_14_2_4_2_2_2_aedisct_fas.rtf	Listing	14.2.4.2.2.2	Non-related adverse events leading to definitive discontinuation of the trial device – Full Analysis Set	L3
L_14_2_4_2_3_1_aediscs_saf.rtf	Listing	14.2.4.2.3.1	Non-related adverse events leading to definitive discontinuation of the study – Safety Set	L3
L_14_2_4_2_3_2_aediscs_fas.rtf	Listing	14.2.4.2.3.2	Non-related adverse events leading to definitive discontinuation of the study – Full Analysis Set	L3
SAFETY – INCIDENTS				
T_14_3_1_1_incsum_saf.rtf	Table	14.3.1.1	Summary of incidents – Safety Set	T17
T_14_3_1_2_incsocpt_saf.rtf	Table	14.3.1.2	Incidents by System Organ Class and Preferred Term – Safety Set	T18
L_14_3_2_1_sinc_saf.rtf	Listing	14.3.2.1	Serious incidents – Safety Set	L3
L_14_3_2_2_incdisct_saf.rtf	Listing	14.3.2.2	Incidents leading to definitive discontinuation of the trial device – Safety Set	L3
L_14_3_2_3_incdiscs_saf.rtf	Listing	14.3.2.3	Incidents leading to definitive discontinuation of the study – Safety Set	L3
PATIENTS DATA LISTINGS				
L_16_2_1_disc.rtf	Listing	16.2.1	Discontinued patients	NA
L_16_2_2_dv.rtf	Listing	16.2.2	Protocol deviations	NA

AXIODIS CRO 29/47

Study Number: LPH-2202

Statistical Analysis Plan BASICC Final version – August 09th, 2023

File (BASICC)	Туре	Number	Title	Mock
L 16_2_3_excl_eff.rtf	Listing	16.2.3	Patients excluded from the efficacy analysis	NA
L_16_2_4_1_dm.rtf	Listing	16.2.4.1	Demographic characteristics by patient	NA
L_16_2_4_2_1_mh.rtf	Listing	16.2.4.2.1	Medical history by patient	NA
L 16 2 4 2 2 mh coded.rtf	Listing	16.2.4.2.2	Medical history events (MedDRA V25.0)	NA
L_16_2_4_3_ie.rtf	Listing	16.2.4.3	Inclusion/Exclusion criteria	NA
L_16_2_4_4_forbidm.rtf	Listing	16.2.4.4	Past or concomitant forbidden medications and concomitant treatments for first symptoms of infectious rhinitis at enrolment / inclusion	NA
L_16_2_4_5_fever.rtf	Listing	16.2.4.5	Fever and body temperature	NA
L_16_2_5_1_sv.rtf	Listing	16.2.5.1	Dates of visits	NA
L_16_2_5_2_rand.rtf	Listing	16.2.5.2	Randomization and product unblinding	NA
L_16_2_5_3_compl.rtf	Listing	16.2.5.3	Compliance to treatment intake	NA
L_16_2_6_1_1_arssq.xml	Listing	16.2.6.1.1	Acute Rhinitis Symptoms Severity Questionnaire	NA
L_16_2_6_1_2_tte.rtf	Listing	16.2.6.1.2	Durations of common cold, of cold symptoms and of impacts on Quality-of-Life	NA
L_16_2_6_2_1_1 cm.rtf	Listing	16.2.6.2.1.1	Previous and concomitant medications by patient	NA
L 16 2 6 2 1 2 cm coded.rtf	Listing	16.2.6.2.1.2	Coded medications (WHO-DRUG 2022 Q1)	NA
L_16_2_6_2_intak.rtf	Listing	16.2.6.2.2	Intakes of common cold medications	NA
L_16_2_6_2_3_cm_end.rtf	Listing	16.2.6.2.3	Concomitant treatments at end of study / premature termination	NA
L 16 2 6 3 symp_end.rtf	Listing	16.2.6.3	Symptoms of acute rhinitis at end of study / premature termination	NA
L_16_2_7_1_ae.rtf	Listing	16.2.7.1	Adverse events and incidents	NA
L 16 2 7 2 ae coded.rtf	Listing	16.2.7.2	Coded adverse events and incidents (MedDRA V25.0)	NA
L 16 2 7 3 ae end.rtf	Listing	16.2.7.3	Adverse events and incidents at end of study / premature termination	NA

AXIODIS CRO 30/47

13.2. Mock tables

Mock T1

[figure not shown]
	Healsea Babykids N=XX	Placebo N=XX	Total N=XX
Analysis Sets			
Enrolled patients	XX (XX.X%)	XX (XX.X%)	XX (XX.X%)
Included patients	XX (XX.X%)	XX (XX.X%)	XX (XX.X%)
Randomised patients	XX (XX.X%)	XX (XX.X%)	XX (XX.X%)
Safety Set	XX (XX.X%)	XX (XX.X%)	XX (XX.X%)
Full Analysis Set	XX (XX.X%)	XX (XX.X%)	XX (XX.X%)
Per Protocol Set	XX (XX.X%)	XX (XX.X%)	XX (XX.X%)

AXIODIS CRO 31/47

Final version – August 09th, 2023

Statistical Analysis Plan

Mock F1

AXIODIS CRO 32/47

Study Number: LPH-2202

BASICC

Statistical Analysis Plan
Final version – August 09th, 2023

Follow-up: Patients Lost to follow-up (give reasons) (N=XX) {list of patients}

Discontinued intervention (give reasons) (N=XX) {list of patients}

Safety Set (N=XX)

Patients excluded from Safety Set (did not take any treatment) (N=XX) {list of patients}

Full Analysis Set Full Analysis Set (N=XX)

Patients excluded from Full Analysis Set (without any post-baseline efficacy data) (N=XX) {list of patients}

Per Protocol Set Per Protocol Set (N=XX)

Patients excluded from Per Protocol Set (with major protocol deviations) (give reasons) (N=XX) {list of patients}

Healsea Babykids arm

Lost to follow-up (give reasons) (N=XX) {list of patients}

Discontinued intervention (give reasons) (N=XX) {list of patients}

Safety Set (N=XX)

Patients excluded from Safety Set (did not take any treatment) (N=XX) {list of patients}

Full Analysis Set (N=XX)

Patients excluded from Full Analysis Set (without any post-baseline efficacy data) (N=XX) {list of patients}

Per Protocol Set (N=XX)

Patients excluded from Per Protocol Set (with major protocol deviations) (give reasons) (N=XX) {list of patients}

Placebo arm

AXIODIS CRO 33/47

Final version – August 09th, 2023

Statistical Analysis Plan

Mock T2

Category of deviation – Type of deviation	Healsea Babykids N=XX	Placebo N=XX	Total N=XX
Patients with at least one protocol deviation	 	'	
All	XX (XX.X%)	XX (XX.X%)	XX (XX.X%)
Major deviations			
All	XX (XX.X%)	XX (XX.X%)	XX (XX.X%)
XXXXX	XX (XX.X%)	XX (XX.X%)	XX (XX.X%)
XXXXX	XX (XX.X%)	XX (XX.X%)	XX (XX.X%)
Minor deviations			
All	XX (XX.X%)	XX (XX.X%)	XX (XX.X%)
XXXXX	XX (XX.X%)	XX (XX.X%)	XX (XX.X%)
XXXXX	XX (XX.X%)	XX (XX.X%)	XX (XX.X%)

Mock L1

ID – Sex – Age	Treatment	Safety Set	Full Analysis Set	Per Protocol Set	Protocol deviation	Classification of deviation

Mock T3

	Healsea Babykids N=XX	Placebo N=XX	Total N=XX
Reason of premature w	ithdrawal		
XXXXXXX	XX (XX.X%)	XX (XX.X%)	XX (XX.X%)

Mock L2

ID – Sex – Age	Treatment	Safety Set	Full Analysis Set	Per Protocol Set	Reason of withdrawal

AXIODIS CRO 34/47 Study Number: LPH-2202

BASICC

Mock T4

	Healsea Babykids N=XX	Placebo N=XX	Total N=XX
Age (years)			
N	XX	XX	XX
Missing	XX	XX	XX
Mean (SD)	XX.X (XX.X)	XX.X (XX.X)	XX.X (XX.X)
Median	XX	XX	XX
Q1/Q3	XX / XX	XX / XX	XX / XX
Min/Max	XX / XX	XX / XX	XX / XX
Sex			
N	XX	XX	XX
Missing	XX	XX	XX
Female	XX (XX.X%)	XX (XX.X%)	XX (XX.X%)
Male	XX (XX.X%)	XX (XX.X%)	XX (XX.X%)

Mock T5

ATC1 - ATC2	Healsea Babykids N=XX	Placebo N=XX	Total N=XX
Patients with at least one previous / concomitant	medication		
All	XX (XX.X%)	XX (XX.X%)	XX (XX.X%)
XXXXX			
All	XX (XX.X%)	XX (XX.X%)	XX (XX.X%)
XXXXX	XX (XX.X%)	XX (XX.X%)	XX (XX.X%)
XXXXX	XX (XX.X%)	XX (XX.X%)	XX (XX.X%)

Mock T6

	Healsea Babyki N=XX	ls Placebo N=XX	Total N=XX
Is the patient currently taking antibiotics or has the patie	nt taken antibiotics within 2 weeks before screenin	g?	•
N	XX	XX	XX
Missing	XX	XX	XX
No	XX (XX.X%) XX (XX.X%)	XX (XX.X%)
Yes	XX (XX.X%) XX (XX.X%)	XX (XX.X%)
Is the patient currently taking systemic corticosteroids or	has the patient taken systemic corticosteroids wit	hin 4 weeks before scree	ening?
N	XX	XX	XX
Missing	XX	XX	XX
No	XX (XX.X%) XX (XX.X%)	XX (XX.X%)
Yes	XX (XX.X%) XX (XX.X%)	XX (XX.X%)
Has the patient a chronic use of decongestant?			
N	XX	XX	XX
Missing	XX	XX	XX
No	XX (XX.X%) XX (XX.X%)	XX (XX.X%)
Yes	XX (XX.X%) XX (XX.X%)	XX (XX.X%)
Has the patient taken any medicine (in the previous 48 ho	ours) that could modify the ARSSQ assessment?		
N	XX	XX	XX
Missing	XX	XX	XX
No	XX (XX.X%) XX (XX.X%)	XX (XX.X%)
Yes	XX (XX.X%) XX (XX.X%)	XX (XX.X%)

AXIODIS CRO 35/47

Statistical Analysis Plan Final version – August 09th, 2023

Mock T7

	Healsea Babykids N=XX	Placebo N=XX	Total N=XX
Has the patient taken / has the patient been prescribed any treatment for first symptoms of	f infectious rhinitis?		
N	XX	XX	XX
Missing	XX	XX	XX
No	XX (XX.X%)	XX (XX.X%)	XX (XX.X%)
Yes	XX (XX.X%)	XX (XX.X%)	XX (XX.X%)

Mock T8

SOC - Preferred Term	Healsea Babykids N=XX	Placebo N=XX	Total N=XX			
Patients with at least one medical history						
All	XX (XX.X%)	XX (XX.X%)	XX (XX.X%)			
XXXXX						
All	XX (XX.X%)	XX (XX.X%)	XX (XX.X%)			
XXXXX	XX (XX.X%)	XX (XX.X%)	XX (XX.X%)			
XXXXX	XX (XX.X%)	XX (XX.X%)	XX (XX.X%)			

AXIODIS CRO 36/47

Mock T9

	Healsea Babykids N=XX	Placebo N=XX	Total N=XX
How sick does your child	I feel today?		
N	XX	XX	XX
Missing	XX	XX	XX
Mean (SD)	XX.X (XX.X)	XX.X (XX.X)	XX.X (XX.X)
Median	XX	XX	XX
Q1/Q3	XX / XX	XX / XX	XX / XX
Min/Max	XX / XX	XX / XX	XX / XX
Between-groups test	XXX (Student/Wilcoxon)		
Runny nose	1		
N	XX	XX	XX
Missing	XX	XX	XX
Mean (SD)	XX.X (XX.X)	XX.X (XX.X)	XX.X (XX.X)
Median	XX	XX	XX
Q1/Q3	XX / XX	XX / XX	XX / XX
Min/Max	XX / XX	XX / XX	XX / XX
Between-groups test	XXX (Student/Wilcoxon)	1217 1211	1227 1211
Stuffy nose / Blocked no	1		ı
N	XX	XX	XX
Missing	XX	XX	XX
Mean (SD)	XX.X (XX.X)	XX.X (XX.X)	XX.X (XX.X)
Median	XX	XX	XX
Q1/Q3	XX/XX	XX / XX	XX / XX
Min/Max	XX / XX	XX / XX	XX / XX
Between-groups test	XXX (Student/Wilcoxon)	AATAA	XX/XX
Yellow / Green discharg	 		
N	XX	XX	XX
Missing	XX	XX	XX
Mean (SD)	XX.X (XX.X)	XX.X (XX.X)	XX.X (XX.X)
Median	XX	XX.X (XX.X) XX	XX
Q1/Q3	XX/XX	XX / XX	XX / XX
Min/Max	XX / XX	XX / XX	XX / XX
		ΑΛ / ΑΛ	AA/AA
Between-groups test	XXX (Student/Wilcoxon)		
Nasal crust (dry mucus)		VV	VV
N M:	XX	XX	XX
Missing	XX	XX	XX
Mean (SD)	XX.X (XX.X)	XX.X (XX.X)	XX.X (XX.X)
Median	XX	XX	XX
Q1/Q3	XX / XX	XX / XX	XX / XX
Min/Max	XX / XX	XX / XX	XX / XX
Between-groups test	XXX (Student/Wilcoxon)		
Sore throat (hurts to sw	, , , , , , , , , , , , , , , , , , , 		
N	XX	XX	XX
Missing	XX	XX	XX
Mean (SD)	XX.X (XX.X)	XX.X (XX.X)	XX.X (XX.X)
Median	XX	XX	XX
Q1/Q3	XX / XX	XX / XX	XX / XX
Min/Max	XX / XX	XX / XX	XX / XX
Between-groups test	XXX (Student/Wilcoxon)		

AXIODIS CRO 37/47

	Healsea Babykids N=XX	Placebo N=XX	Total N=XX
Sneezing / Cough	1		
N	XX	XX	XX
Missing	XX	XX	XX
Mean (SD)	XX.X (XX.X)	XX.X (XX.X)	XX.X (XX.X)
Median	XX	XX	XX
Q1/Q3	XX / XX	XX / XX	XX / XX
Min/Max	XX / XX	XX / XX	XX / XX
Between-groups test	XXX (Student/Wilcoxon)		
Cold symptoms	/		
N	XX	XX	XX
Missing	XX	XX	XX
Mean (SD)	XX.X (XX.X)	XX.X (XX.X)	XX.X (XX.X)
Median	XX	XX	XX
Q1/Q3	XX / XX	XX / XX	XX / XX
Min/Max	XX / XX	XX / XX	XX / XX
Between-groups test	XXX (Student/Wilcoxon)	AA / AA	AXTAX
Impact on Sleeping	2222 (Student Wilcoxoll)		 
N Sleeping	XX	XX	XX
Missing	XX	XX	XX
Mean (SD)	XX.X (XX.X)	XX.X (XX.X)	XX.X (XX.X)
Median (SD)	XX	XX.X (XX.X)	XX
Q1/Q3	XX / XX	XX / XX	XX / XX
Min/Max	XX / XX	XX / XX	XX / XX
Between-groups test	XXX (Student/Wilcoxon)		
Impact on Breathing	NA.		7/7/
N	XX	XX	XX
Missing	XX	XX	XX
Mean (SD)	XX.X (XX.X)	XX.X (XX.X)	XX.X (XX.X)
Median	XX	XX	XX
Q1/Q3	XX / XX	XX / XX	XX / XX
Min/Max	XX / XX	XX / XX	XX / XX
Between-groups test	XXX (Student/Wilcoxon)		
	ng to the nursery or to school		
N	XX	XX	XX
Missing	XX	XX	XX
Mean (SD)	XX.X (XX.X)	XX.X(XX.X)	XX.X (XX.X)
Median	XX	XX	XX
Q1/Q3	XX / XX	XX / XX	XX / XX
Min/Max	XX / XX	XX / XX	XX / XX
Between-groups test	XXX (Student/Wilcoxon)		
Impact on Quality-of-Li	fe		
N	XX	XX	XX
Missing	XX	XX	XX
Mean (SD)	XX.X (XX.X)	XX.X (XX.X)	XX.X (XX.X)
Median	XX	XX	XX
Q1/Q3	XX / XX	XX / XX	XX / XX
Q1/Q3	1		
Min/Max	XX / XX	XX / XX	XX / XX

AXIODIS CRO 38/47

	Healsea Babykids N=XX	Placebo N=XX	Total N=XX
N	XX	XX	XX
Missing	XX	XX	XX
Mean (SD)	XX.X (XX.X)	XX.X (XX.X)	XX.X (XX.X)
Median	XX	XX	XX
Q1/Q3	XX / XX	XX / XX	XX / XX
Min/Max	XX / XX	XX / XX	XX / XX
Between-groups test	XXX (Student/Wilcoxon)		

Mock T10

	Healsea Babykids N=XX	Placebo N=XX	Total N=XX
Has the patient fever?			
N	XX	XX	XX
Missing	XX	XX	XX
No	XX (XX.X%)	XX (XX.X%)	XX (XX.X%)
Yes	XX (XX.X%)	XX (XX.X%) XX (XX.X%)	
Between-groups test	XXX (Chi-2/Fisher)		
Body temperature (°C)			
N	XX	XX	XX
Missing	XX	XX	XX
Mean (SD)	XX.X (XX.X)	XX.X (XX.X)	XX.X (XX.X)
Median	XX	XX	XX
Q1/Q3	XX / XX	XX / XX	XX / XX
Min/Max	XX / XX	XX / XX	XX / XX
Between-groups test	XXX (Student/Wilcoxon)		

Mock T11

	Healsea Babykids N=XX	Placebo N=XX	Total N=XX
Compliance (%)			
N	XX	XX	XX
Missing	XX	XX	XX
Mean (SD)	XX.X (XX.X)	XX.X (XX.X)	XX.X (XX.X)
Median	XX	XX	XX
Q1/Q3	XX / XX	XX / XX	XX / XX
Min/Max	XX / XX	XX / XX	XX / XX
Compliance category			
N	XX	XX	XX
Missing	XX	XX	XX
<80%	XX (XX.X%)	XX (XX.X%)	XX (XX.X%)
[80%; 120%]	XX (XX.X%)	XX (XX.X%)	XX (XX.X%)
>120%	XX (XX.X%)	XX (XX.X%)	XX (XX.X%)

AXIODIS CRO 39/47

Mock T12

[figure not shown]
	Healsea Babykids N=XX	Placebo N=XX	Total N=XX
Study duration (days)		
N	XX	XX	XX
Missing	XX	XX	XX
Mean (SD)	XX.X (XX.X)	XX.X (XX.X)	XX.X (XX.X)
Median	XX	XX	XX
Q1/Q3	XX / XX	XX / XX	XX / XX
Min/Max	XX / XX	XX / XX	XX / XX
Treatment duration (days)		
N	XX	XX	XX
Missing	XX	XX	XX
Mean (SD)	XX.X (XX.X)	XX.X (XX.X)	XX.X (XX.X)
Median	XX	XX	XX
Q1/Q3	XX / XX	XX / XX	XX / XX
Min/Max	XX / XX	XX / XX	XX / XX
Patients who stopped	treatment	·	
N	XX	XX	XX
Missing	XX	XX	XX
Before D8	XX (XX.X%)	XX (XX.X%)	XX (XX.X%)
At D8 morning	XX (XX.X%)	XX (XX.X%)	XX (XX.X%)
At D8 evening	XX (XX.X%)	XX (XX.X%)	XX (XX.X%)
At D9 morning	XX (XX.X%)	XX (XX.X%)	XX (XX.X%)
At D9 evening	XX (XX.X%)	XX (XX.X%)	XX (XX.X%)
At D10 morning	XX (XX.X%)	XX (XX.X%)	XX (XX.X%)
At D10 evening	XX (XX.X%)	XX (XX.X%)	XX (XX.X%)
At D11 morning	XX (XX.X%)	XX (XX.X%)	XX (XX.X%)
At D11 evening	XX (XX.X%)	XX (XX.X%)	XX (XX.X%)
At D12 morning	XX (XX.X%)	XX (XX.X%)	XX (XX.X%)
At D12 evening	XX (XX.X%)	XX (XX.X%)	XX (XX.X%)
After D12	XX (XX.X%)	XX (XX.X%)	XX (XX.X%)

AXIODIS CRO 40/47

Mock T13

	Healsea Babykids N=XX	Placebo N=XX	Total N=XX
AUC on global score of ARSSQ			
N	XX	XX	XX
Missing	XX	XX	XX
Mean (SD)	XX.X (XX.X)	XX.X(XX.X)	XX.X (XX.X)
Median	XX	XX	XX
Q1/Q3	XX / XX	XX / XX	XX / XX
Min/Max	XX / XX	XX / XX	XX / XX
Between-groups test	XXX (Student/Wilcoxon)		

Mock F2

AXIODIS CRO 41/47

Mock T14

[figure not shown]
	Healsea Babykids N=XX	Placebo N=XX
AUC on global score of ARSSQ		
ANCOVA model :		
AUC = Treatment +		
Type 3 Tests of Fixed Effects		
Treatment	XXX	
	XXX	
Adjusted mean		
LSMeans (SE)	XX.X (XX.X)	XX.X (XX.X)
[LSM 95%CI]	[XX.X; XX.X]	[XX.X; XX.X]
Adjusted mean (diff. vs Placebo)		
LSMeans (SE)	XX.X (XX.X)	
[LSM 95%CI]	[XX.X; XX.X]	
Contrast vs Placebo, p=	XXX	

Mock T15

	Healsea Babykids N=XX	Placebo N=XX
Duration of common cold / cold symptoms / impact of	on Quality-of-Life	
N	XX	XX
Missing	XX	XX
Mean (SD)	XX.X (XX.X)	XX.X (XX.X)
Median	XX	XX
Q1/Q3	XX / XX	XX / XX
Min/Max	XX / XX	XX / XX
Cox survival regression model:		
Hazard Ratios [95%CI]		
Treatment	XX.X [XX.X; XX.X]	
	XX.X [XX.X; XX.X]	
p-values (Wald)		
Treatment	XXX	
	XXX	

AXIODIS CRO 42/47

[figure not shown]
Mock F3

For Treatment: the reference is Placebo

AXIODIS CRO 43/47

Mock F4

AXIODIS CRO 44/47

Mock T16

	Healsea Babykids N=XX	Placebo
Use of XXX	N=XX	N=XX
N	XX	XX
Missing	XX	XX
No	XX.X (XX.X%)	XX.X (XX.X%)
Yes	XX.X (XX.X%)	XX.X (XX.X%)
Logistic model :		,
Odds Ratios [95%CI]		
Treatment	XX.X [XX.X; XX.X]	
	XX.X [XX.X; XX.X]	
p-values (Wald)		
Treatment	XXX	
	XXX	
Number of days of intakes of XXX		
N	XX	XX
Missing	XX	XX
0	XX.X (XX.X%)	XX.X (XX.X%)
1	XX.X (XX.X%)	XX.X (XX.X%)
2	XX.X (XX.X%)	XX.X (XX.X%)
	XX.X (XX.X%)	XX.X (XX.X%)
Poisson regression :		
Type 3 Tests of Fixed Effects		
Treatment	XXX	
	XXX	

AXIODIS CRO 45/47

Mock T17

	Healsea Babykids N=XX		ls Placebo N=XX		Total N=XX	
	n (%)	[E]	n (%)	[E]	n (%)	[E]
Number and percentage of patients with / Number of (non-related)						
Incident (Adverse event)	XX (XX.X%)	XXX	XX (XX.X%)	XXX	XX (XX.X%)	XXX
Incident (Adverse event) leading to definitive study device discontinuation	XX (XX.X%)	XXX	XX (XX.X%)	XXX	XX (XX.X%)	XXX
Incident (Adverse event) leading to definitive study discontinuation	XX (XX.X%)	XXX	XX (XX.X%)	XXX	XX (XX.X%)	XXX
Serious incident (adverse event)	XX (XX.X%)	XXX	XX (XX.X%)	XXX	XX (XX.X%)	XXX
(Treatment-emergent adverse event)	XX (XX.X%)	XXX	XX (XX.X%)	XXX	XX (XX.X%)	XXX
(Serious treatment-emergent adverse event)	XX (XX.X%)	XXX	XX (XX.X%)	XXX	XX (XX.X%)	XXX

Mock T18

	Healsea Baby	ykids	Placebo N=XX		Total N=XX	
SOC - Preferred Term	n (%)	[E]	n (%)	[E]	n (%)	[E]
Incidents (Non-related treatment-emergent ad	dverse events)					
All	XX (XX.X%)	XXX	XX (XX.X%)	XXX	XX (XX.X%)	XXX
XXXXX						
All	XX (XX.X%)	XXX	XX (XX.X%)	XXX	XX (XX.X%)	XXX
XXXXX	XX (XX.X%)	XXX	XX (XX.X%)	XXX	XX (XX.X%)	XXX
XXXXX	XX (XX.X%)	XXX	XX (XX.X%)	XXX	XX (XX.X%)	XXX

Mock L3

ID – Sex – Age	Treatment	Incident (Adverse event)	Start date / end date	Ongoing at the end of the study	Intensity	Serious	Action taken	Causality

AXIODIS CRO 46/47

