14.2 Definitions

Incident means any malfunction or deterioration in the characteristics or performance of a device made available on the market, including use-error due to ergonomic features, as well as any inadequacy in the information supplied by the manufacturer and any undesirable side-effect (MDR 2017/745).

Serious incident means any incident that directly or indirectly led, might have led or might lead to any of the following: (a) the death of a patient, user or other person, (b) the temporary or permanent serious deterioration of a patient's, user's or other person's state of health, (c) a serious public health threat (MDR 2017/745).

Serious public health threat means an event which could result in imminent risk of death, serious deterioration in a person's state of health, or serious illness, that may require prompt remedial action,

and that may cause significant morbidity or mortality in humans, or that is unusual or unexpected for the given place and time (MDR 2017/745).

Expected and foreseeable side effects (MEDDEV 2 12-1 rev. 8)

They meet all the following criteria:

- Clearly identified in the manufacturer's labelling,
- Clinically well known as being foreseeable and having a certain qualitative and quantitative predictability when the device is used and performs as intended,
- Documented in the device master record, with an appropriate risk assessment, prior to the occurrence of the incident and,
- Clinically acceptable in terms of the individual patient benefit.

Adverse event means any untoward medical occurrence, unintended disease or injury or any untoward clinical signs, including an abnormal laboratory finding, in subjects, users or other persons, in the context of a clinical investigation, whether related or not related to the investigational device (MDR 2017/745).

Adverse or intercurrent events are graded as follows:

- Mild: Awareness of signs or symptoms but easily tolerated.
- Moderate: Uncomfortable enough to cause interference with usual activity.
- Severe: Incapacity with inability to work or do usual activity.

Serious adverse event (SAE) (MDR Article 2(58)):

Any adverse event that led to any of the following:

- a) death,
- b) serious deterioration in the health of the subject, that resulted in any of the following:
 - i. life-threatening illness or injury,
 - ii. permanent impairment of a body structure or a body function,
 - iii. hospitalisation or prolongation of patient hospitalisation,

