10.4. Non-related adverse events

In the following paragraph, for a smoother reading:

- adverse events will be referred as AE;
- treatment-emergent adverse events will be referred as TEAE.

Adverse events are coded using the MedDRA dictionary version 25.0. They are classified by System Organ Class and Preferred Term.

For efficacy analyses, only non-related AEs are considered, i.e. adverse events with a relationship to study device equal to "not related". These analyses will be performed on the Safety Set and on the FAS, by treatment group and overall.

An adverse event will be considered as a treatment-emergent adverse event (TEAE) if:

- it was reported at least one day after screening;
- it was not present prior to the reference start date;
- it was present prior to the reference start date and worsened during the study (increase of intensity);
- it reappears after the reference start date (finished before the reference start date).

Missing or incomplete dates will be estimated as described in §6.4.4 in order to determine the TEAEs, but they will be presented as reported in CRF in the data listings. Generally, an adverse event for which the onset date is missing or incomplete and does not permit to identify the onset according to the date of the reference start date (i.e. missing onset day and month/year corresponding to the reference start date) will be considered as treatment-emergent.

Note: if the intensity/severity is missing, a conservative approach will be adopted and the intensity/severity will be considered as severe.

A given treatment-emergent adverse event (according to the MedDRA terminology) will be counted only once per patient. If a patient experienced several AEs in the same SOC/PT, the most severe intensity will be retained for this SOC/PT.

Summary of non-related adverse events

A summary table will be produced:

- number and percentage of patients with at least one non-related adverse event (AE);
- number and percentage of patients with at least one non-related AE leading to definitive study device discontinuation;
- number and percentage of patients with at least one non-related AE leading to definitive study discontinuation;
- number and percentage of patients with at least one serious non-related AE;
- number and percentage of patients with at least one non-related TEAE;
- number and percentage of patients with at least one serious non-related TEAE.

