The number of non-related AEs of each category will also be provided in this table.

AXIODIS CRO 22/47

Statistical Analysis Plan Final version – August 09th, 2023

Analysis of non-related treatment-emergent adverse event

The number and percentage of patients with non-related TEAEs will be summarised by System Organ Class and Preferred term.

The number of non-related TEAEs of each category will also be provided in this table.

A listing of serious non-related AEs will be provided.

All non-related AEs leading to definitive discontinuation of the trial device or to definitive discontinuation of the study will be listed.

AXIODIS CRO 23/47

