11.2. Incidents

For safety analyses, only incidents are considered, i.e. adverse events with a relationship to study device other than "not related".

Summary of incidents

A summary table will be produced:

- number and percentage of patients with at least one incident;
- number and percentage of patients with at least one incident leading to definitive study device discontinuation;
- number and percentage of patients with at least one incident leading to definitive study discontinuation;
- number and percentage of patients with at least one serious incident.

The number of incidents of each category will also be provided in this table.

Analysis of incident

The number and percentage of patients with incidents will be summarised by System Organ Class (SOC) and Preferred term (PT).

The number of incidents of each category will also be provided in this table.

A listing of serious incidents will be provided.

All incidents leading to definitive discontinuation of the trial device or to definitive discontinuation of the study will be listed.

AXIODIS CRO 24/47

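### SAP 10.4 keeps each child's worst intensity within SOC/PT, but none of the six adverse-event and incident tables shows intensity, so severity is not summarised by arm

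*SAP*

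**What the plan says.** **Grading.** Protocol 14.2 sets up a three-level scale, introduced by "Adverse or intercurrent events are graded as follows". The levels are mild, moderate and severe, and they are defined by how far the event disturbs the child's usual activity.

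**Rules on intensity.** SAP 10.4, which covers events judged not related to the device, uses intensity in three places:
- missing grades: "if the intensity/severity is missing, a conservative approach will be adopted and the intensity/severity will be considered as severe";
- repeated events: "If a patient experienced several AEs in the same SOC/PT, the most severe intensity will be retained for this SOC/PT";
- the definition of a treatment-emergent adverse event (TEAE), one branch of which is that "it was present prior to the reference start date and worsened during the study (increase of intensity").

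SAP 11.2, which covers incidents (events with any relationship to the device other than not related), states no intensity rule.

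**Planned tables.** For non-related events SAP 10.4 says: "The number and percentage of patients with non-related TEAEs will be summarised by System Organ Class and Preferred term". For incidents SAP 11.2 says: "The number and percentage of patients with incidents will be summarised by System Organ Class (SOC) and Preferred term (PT"). Each section also has a summary table. The list of outputs in SAP 13.1 assigns all of these tables to Mocks T17 and T18. In SAP 13.2, the row label of Mock T18 is "SOC - Preferred Term".

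**Objective.** Protocol 6.3 and SAP 2.2 give the safety objective as tolerance of the device, both systemic and local.

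**The concern.** A rule that picks the worst of several grades within a class and term is a tabulation rule. It serves a SOC/PT table split by intensity, and no such table is planned. A programmer who follows SAP 10.4 derives a variable that goes nowhere.

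The gap matters because of what the tables are for. Protocol 5.2 expects no side effects from either spray, so the listings of serious events and of events that end treatment or participation may be nearly empty. What remains to describe tolerance is the non-serious local events, and for those the grade carries much of the information. By the protocol's own definitions, a mild event is easily tolerated and a moderate one interferes with usual activity. Two arms with the same number of affected children but different grades could look alike in the planned tables.

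**Working it through.** The check compares the rules with the outputs. The plan gives no figure to reproduce.

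**Step 1. Which tables could show intensity?** SAP 13.1 lists six adverse-event or incident tables. SAP 13.2 gives their shells.

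| Table | Content | Set | Mock | Intensity shown |
|---|---|---|---|---|
| 14.2.4.1.1.1 | Summary, non-related events | Safety | T17 | No |
| 14.2.4.1.1.2 | Summary, non-related events | FAS | T17 | No |
| 14.2.4.1.2.1 | Non-related TEAEs by SOC/PT | Safety | T18 | No |
| 14.2.4.1.2.2 | Non-related TEAEs by SOC/PT | FAS | T18 | No |
| 14.3.1.1 | Summary, incidents | Safety | T17 | No |
| 14.3.1.2 | Incidents by SOC/PT | Safety | T18 | No |

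The T17 rows are any event, events that end device use, events that end participation, serious events and, for non-related events, TEAEs and serious TEAEs. The T18 rows are an overall row, then class, then term, each with the number and percentage of children and the number of events. The count is 0 of 6. The text of SAP 10.4 and 11.2, the output list and the shells all agree, so this is not a fault of the text extraction.

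**Step 2. Does the worst-intensity rule change any number?** T18 counts a child once per term and counts events separately. Neither number depends on which grade is kept, and T17 does not use the grade. The rule changes no count.

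**Step 3. Does the missing-as-severe rule change any number?** It can. A rise in intensity can make a pre-existing event treatment-emergent. If a later missing grade is set to severe, a rise may appear; if an earlier missing grade is set to severe, a rise may be hidden. This reaches the TEAE rows of T17 and the non-related version of T18. It does not produce a severity result.

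**Step 4. Where does the grade appear?**
- Mock L3 has an intensity column and a treatment column. SAP 13.1 uses it for nine listings (six for non-related events, three for incidents), limited to serious events and events that end device use or participation.
- Listings 16.2.7.1 and 16.2.7.2 carry titles that cover all adverse events and incidents. Their mock is marked NA, so an intensity column is neither shown nor excluded.

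Neither source gives a summary of severity by arm.

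**Step 5. Illustration (assumed event numbers).** Take the planned 100 children per arm. Let 10 in each arm have a local incident, of which 6 and 1 are moderate or severe.
- Any incident: 10/100 = 10.0% in both arms.
- Moderate or severe: 6/100 = 6.0% against 1/100 = 1.0%.
- Among affected children: 6/10 = 60% against 1/10 = 10%.

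The any-incident row of T17 shows 10 (10.0%) twice. T17 and T18 as a whole print identically only if the numbers of events, the preferred terms, and the serious and discontinuation rows also match. Equal incidence alone does not ensure that.

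**The case against.** The strongest case against the point is that no commitment is broken. Protocol 8.4 promises occurrences and the number and percentage of children by arm, class and term, and T17 and T18 deliver that. SAP 6.3.1 treats everything beyond the primary criterion as descriptive. If incidents are few, a complete listing may be enough for a reader to judge severity. On this view an added table is a preference, and deleting the unused rule would also make the SAP consistent.

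Much of this stands, and it rules out several stronger readings that a reader might infer:
- **That the grade of non-serious events is reported nowhere.** The documents do not show this, because Listings 16.2.7.1 and 16.2.7.2 may carry it. What is missing is a summary by arm.
- **That both intensity rules are idle.** Only the worst-intensity rule is. The missing-as-severe rule can bear on TEAE status.
- **That SAP 11.2 contains an unused rule.** The unused rule is in 10.4, which covers non-related events that the SAP places under efficacy. Section 11.2 has no intensity rule, so for incidents the gap is an omission.
- **That the SAP departs from the protocol.** The protocol asks for no severity table.

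What does not stand is that the gap can be left alone. The final SAP defines a derivation with no use, and it does not say whether the same handling applies to incidents, which are the device-related tolerance data. Deleting the rule would tidy the text but leave severity unsummarised under a tolerance objective.

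**Conclusion.** The point holds as a gap between the SAP's own rules and its outputs. None of the six tables shows intensity, the worst-intensity rule in 10.4 feeds none of them, and severity is not summarised by arm for non-related TEAEs or for incidents.

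Its reach is limited to the description of tolerance. The primary analysis and the planned counts of events, serious events and discontinuations are unaffected. How much information is lost depends on how many non-serious events occur and how their grades fall in the two arms, which the documents do not predict. The conclusion assumes that the outputs are those listed in SAP 13.1 with the shells in 13.2. The change is worth making because the grades are already defined and a derivation rule is already written.

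**What to change.** 1. **Mock T18:** within each class and term, add the number and percentage of children by worst intensity (mild, moderate, severe), by arm and in total. Use it for non-related TEAEs and for incidents.
2. **Mock T17:** add a row for children with at least one severe event, by arm and in total: severe non-related TEAE in one version and severe incident in the other.
3. **SAP 11.2:** state in one sentence that the two intensity rules of 10.4 also apply to incidents.
4. **Missing grades:** show how many entries counted as severe come from a missing grade, so that observed and imputed severe events can be told apart.

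The cost is two revised shells, one sentence and slightly longer tables. No new data are needed. The output is descriptive and uses no type I error.
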